13.6 Analysis of Secondary Endpoints

Complete response rate, duration of response, duration of complete response, progression free survival, and overall survival will be reported for the entire cohort.

Response rates will be tabulated and reported as proportions with 90% exact binomial confidence intervals for each point estimate. Time-to-event endpoints will be assessed using the method of Kaplan and Meier; follow-up time will be estimated using the reverse Kaplan-Meier

method; estimates will be reported along with 90% confidence intervals where estimable using Greenwood's formula to calculate variance.

As secondary analyses, additional response criteria may be used to estimate response rates, and these rates will be assessed and reported as described above.

Sub-populations of patients may also be analyzed for by histology for response and time-to-event endpoints if sample sizes are sufficient. The methods described above will be used to report corresponding endpoints.

Abnormal laboratory test results and attributions to study drug will be summarized.

13.6.1 Safety analyses

Safety evaluations will be performed for the total cohort of patients including all who received at least one dose of study treatment. Incidence, severity, and type of adverse events (AEs) will be tabulated and reported as proportions.

SAEs, deaths, and other safety-related events resulting in discontinuation from study will be reported separately.

Safety analyses may also be performed by sub-populations of patients depending on the size of each.

13.6.2 Correlative analyses

Correlative studies examining the relationship between PD-1/PD-L1/PD-L2 expression, immune microenvironment, and circulating lymphocyte with outcome will be performed where samples are available. The exact studies to be performed are subject to sample and funding availability. In the case of insufficient sample size for meaningful statistical analyses, correlative data will be reported with descriptive statistics.

13.7 Reporting and Exclusions

The primary analyses will be on an intent-to-treat basis, considering all patients who are enrolled on study. Secondary analyses and toxicity analyses will be performed on the subset of eligible patients who received at least 1 dose of study drug.

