1.2 Primary Objectives

- To examine the efficacy (overall response rate) of pembrolizumab in patients with biologically selected subsets of relapsed/refractory (R/R) biologically selected subgroups of lymphoma, using 2014 Lugano criteria (31, appendix C).

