1.3 Secondary Objectives

- To examine the rates of complete response, partial response, stable disease, and progressive disease with pembrolizumab in the group of patients with biologically selected subsets of R/R biologically selected subgroups of lymphoma and histiocyte/dendritic cell neoplasms, using the 2014 Lugano criteria (31, appendix C)
- To examine the efficacy (overall response rate) of pembrolizumab in patients with histiocytic sarcoma, follicular dendritic cell sarcoma, and interdigitating dendritic cell sarcoma using 2014 Lugano criteria (31, appendix C).
- To examine the duration of response, duration of complete response, and progression-free survival associated with pembrolizumab treatment in this patient population, using the 2014 Lugano criteria (31, appendix C).
- To examine the rates of overall, complete and partial response as well as stable disease, progression-free survival and duration of remission using the LyRIC criteria [32, appendix B]
- To examine the safety and toxicity of pembrolizumab in patients with biologically selected subsets of R/R lymphoma and histiocyte/dendritic cell neoplasms.

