13.2 Sample Size, Accrual Rate and Study Duration

13.2.1 Sample size

The study will be powered based on the number of patients with EBV+ DLBCL enrolled. Patients with other allowed lymphoma histologies will be enrolled until the accrual goal of 20 patients with EBV+ DLBCL/TCHRLCL/plasmablastic lymphoma is met (with a maximum of 10 patients in any given lymphoma histology) at which time accrual to all lymphoma cohorts will close. The exact number of patients enrolled depends on the accrual of non-EBV+ DLBCL patients, but is expected to be 24-30 patients. If by the time 20 patients with EBV+ DLBCL are accrued, the total accrual is <24, accrual will continue to all 3 cohorts (including EBV+ DLBCL) until the total accrual reaches 24.

Six patients with histiocytic sarcoma, follicular dendritic cell sarcoma, and/or interdigitating dendritic cell sarcoma will be included in the trial and accrual to this subgroup can continue independent of closure of the study to accrual of lymphoma patients. Given the extremely rare

nature of these diseases, these patients are being included for exploratory purposes only and the statistics of the trial will not be powered based upon this patient population.

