13.5 Analysis of Primary Endpoints

Primary and secondary analyses will be performed on all patients who had measurable disease present at baseline, received at least one cycle of study drug, and had their disease re-evaluated for response. Response rates will be tabulated and reported as proportions with 90% exact binomial confidence intervals for each point estimate.

See Section 11 for additional details and definitions.

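### The primary analysis set and the 6-responder rule carry no disease restriction, so responders among the six exploratory histiocytic/dendritic cell patients could count toward a lymphoma-only primary objective

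*Combined protocol and SAP*

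**What the plan says.** Three sections of the combined protocol and SAP separate the two disease groups.

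- Section 1.2 sets the primary response-rate objective "in patients with biologically selected subsets of relapsed/refractory (R/R) biologically selected subgroups of lymphoma". It does not name histiocytic or dendritic cell disease.
- Section 1.3 has a separate secondary objective: "To examine the efficacy (overall response rate) of pembrolizumab in patients with histiocytic sarcoma, follicular dendritic cell sarcoma, and interdigitating dendritic cell sarcoma".
- Section 13.2.1 states: "Six patients with histiocytic sarcoma, follicular dendritic cell sarcoma, and/or interdigitating dendritic cell sarcoma will be included in the trial". It adds that "these patients are being included for exploratory purposes only" and leaves them out of the powering.

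The sections that define the primary analysis do not make this separation.

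- Section 13.5: "Primary and secondary analyses will be performed on all patients who had measurable disease present at baseline", provided they also received at least one cycle and were re-evaluated.
- Section 13.7: "The primary analyses will be on an intent-to-treat basis, considering all patients who are enrolled on study".
- Section 13.1 names overall response rate as the primary endpoint without a population.
- Section 13.2.2 calls the treatment promising if at least 6 patients respond, assuming at least 20 are enrolled, and does not say which diseases those patients have.

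Measurable disease is an eligibility criterion for everyone (3.1.12), so the six can satisfy 13.5 as well as 13.7.

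**The concern.** An analyst who follows 13.7 counts the six patients, and one who follows 1.2 and 13.2.1 leaves them out. The plan does not say which is right. The trial is open-label, so the choice could be made after responses are known, and a prespecified analysis set exists to prevent that.

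The decision rule is at stake. It is a count of responders with a low bar, and a single responder from outside the primary objective can be enough to reach it. The headline response rate would also describe a mixture of diseases and not the population named in 1.2. Resolving the separate disagreement between 13.5 (re-evaluated patients) and 13.7 (all enrolled patients) would not settle this point, because neither definition mentions disease.

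**Working it through.** **Inputs.** From 13.2.2: 20 patients, success at 6 or more responders, null rate 15%, alternative 40%, stated significance level 0.07, stated power about 87%. From 13.2.1: six histiocytic/dendritic cell patients. The true response rate in those six, *q*, is not given in the documents. I take 5%, 15% and 30% as an assumed range, with 0% as the limiting case.

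**Step 1: reproduce the plan's figures.** With lymphoma responders L ~ Bin(20, p):

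- P(L ≥ 6 | p = 0.15) = 0.067, which is 0.07 at the two decimals given.
- P(L ≥ 6 | p = 0.40) = 0.874, which is the stated 87%.

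The sidedness is not stated; the one-sided upper tail reproduces the figures. Neighbouring cutoffs do not fit: 5 or more gives 0.170 and 0.949, and 7 or more gives 0.022 and 0.750.

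**Step 2: add the six and leave the rule unchanged.** Let H ~ Bin(6, q), independent of L. Then

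P(L + H ≥ 6) = P(L ≥ 6) + Σ P(L = a) × P(H ≥ 6 − a), summed over a = 0 to 5.

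The sum is the probability that lymphoma alone misses the bar and responders among the six carry the total over it. With lymphoma held at 20 patients and p = 0.15:

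| Assumed q | P(L ≥ 6) | Added by the six | P(L + H ≥ 6) |
|---|---|---|---|
| 0% | 0.067 | 0 | 0.067 |
| 5% | 0.067 | 0.034 | 0.101 |
| 15% | 0.067 | 0.118 | 0.185 |
| 30% | 0.067 | 0.276 | 0.343 |

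The q = 15% row can be checked directly, since both groups then share one rate: P(Bin(26, 0.15) ≥ 6) = 0.185.

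**Step 3: one concrete case.** 5 responders among 20 lymphoma patients miss the bar. 5/20 plus 1/6 gives 6/26 and meets it.

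**Step 4: the other direction.** Suppose 8 of 20 lymphoma patients respond and none of the six does. The estimate moves from 8/20 = 40% (exact 90% CI 21.7% to 60.6%) to 8/26 = 31% (16.3% to 48.7%). Both totals are at least 6, so the decision is the same.

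**Step 5: what restricting to lymphoma achieves.** With lymphoma only and the cutoff still at 6, the chance of success at a true 15% is 0.067 at 20 patients, 0.139 at 24 and 0.289 at 30. Section 13.2.1 expects 24 to 30 patients and does not make clear whether the six are part of that total. Restriction therefore removes the effect in Step 2 but returns the stated 0.07 only at 20 lymphoma patients.

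**The case against.** The strongest reply is that neither 13.5 nor 13.7 mentions the six patients. Section 13.7 is about intent-to-treat against treated patients, and 13.5 is about evaluability. The passages that do deal with disease all point toward exclusion, and a statistician who lets the specific govern the general would leave the six out. This stands to the extent that a reader might infer an instruction to pool from 13.5 and 13.7, and the documents do not support that inference. What they contain is an unreconciled contradiction. The reply does not remove it: calling the patients exploratory and outside the powering explains why they are enrolled and how the sample size was set, but no sentence takes them out of the primary response rate.

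Three further points against a stronger reading also stand.

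- A reader might infer that non-responders among the six could overturn a positive lymphoma result. Under a rule that counts responders they cannot; they only lower the estimate.
- A reader might attribute all the error inflation in this trial to mixing diseases. Much of it can come from a cutoff fixed at 6 when more than 20 lymphoma patients are enrolled, which is a separate matter.
- A reader might extend the criticism to 13.6, where complete response, duration of response, progression-free and overall survival "will be reported for the entire cohort". That does not follow. Section 1.3 sets response-category rates in lymphoma and histiocyte/dendritic cell neoplasms together as a secondary objective, and 13.6 already allows analysis by histology if numbers suffice.

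It is also fair that the size rests on an assumed response rate. At 0% the decision is untouched, and at 5% the probability moves only from 0.067 to 0.101.

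**Conclusion.** The contradiction is real and bears on the primary conclusion. Sections 13.5, 13.7 and 13.2.2 place no disease limit on the primary response rate or the responder rule, while 1.2, 1.3 and 13.2.1 treat the six patients as outside the primary question. Followed literally, the analysis sections let those patients' responses count.

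The size is conditional on 20 lymphoma patients at a true 15%, all six extra patients counted, independence between the groups, and a response rate among the six that the documents do not supply. Over the assumed 5% to 30%, the chance of a false promising result is about 1.5 times (0.101/0.067) to 5.1 times (0.343/0.067) that of the lymphoma-only rule.

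**What to change.** In 13.5 and 13.7, state that the primary overall response rate is computed in lymphoma patients only. In 13.2.2, state that the responders counted toward the bar of 6 are lymphoma patients. Add that the response rate in the six histiocytic/dendritic cell patients is reported separately with an exact 90% binomial interval. That delivers the 1.3 objective, which the histology list in 13.3 currently omits.

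Leave the entire-cohort reporting in 13.6 as it is.

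The cost is a few clauses in an amendment, with no new patients, data or assessments. The sponsor should deal separately with how the cutoff relates to the number of lymphoma patients enrolled, since this wording change alone does not hold the level at 0.07 beyond 20.

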4. REGISTRATION PROCEDURES

4.1 General Guidelines for DF/HCC Institutions

Institutions will register eligible participants in the Clinical Trials Management System (CTMS) OnCore. Registrations must occur prior to the initiation of protocol therapy. Any participant not registered to the protocol before protocol therapy begins will be considered ineligible and registration will be denied.

An investigator will confirm eligibility criteria and a member of the study team will complete the protocol-specific eligibility checklist.

Following registration, participants may begin protocol therapy. Issues that would cause treatment delays should be discussed with the Overall Principal Investigator (PI). If a participant does not receive protocol therapy following registration, the participant's registration on the study must be canceled. Registration cancellations must be made in OnCore as soon as possible.

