13. STATISTICAL CONSIDERATIONS

13.1 Study Design/Endpoints

This study is an open-label phase II clinical trial. The primary endpoint is overall response rate. Secondary end points include examining the overall and complete response rates of pembrolizumab in the subgroup of patients with biologically selected subtypes of relapsed and refractory diffuse large B-cell lymphoma. We will also describe the safety and toxicity of pembrolizumab in patients with biologically selected subsets of relapsed and refractory diffuse large B-cell lymphoma. We will also report the complete response rate, duration of response, duration of complete response, progression free survival, and overall survival.

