3.8.2 Definitions

Protocol Deviation: Any departure from the defined procedures set forth in the IRB-approved protocol which is *prospectively approved* prior to its implementation.

Protocol Exception: Any protocol deviation that relates to the eligibility criteria, e.g. enrollment of a participant who does not meet all inclusion/exclusion criteria.

Protocol Violation: Any protocol deviation that was not *prospectively approved* by the IRB prior to its initiation or implementation.

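### Sections 13.6.1 and 13.7 set conflicting safety populations, and 13.6.1 ties its discontinuation category to leaving the study rather than stopping protocol therapy

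*Combined protocol and SAP*

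**What the plan says.** Two sections give a population for safety or toxicity.

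- Section 13.6.1: "Safety evaluations will be performed for the total cohort of patients including all who received at least one dose of study treatment".
- Section 13.7: "Secondary analyses and toxicity analyses will be performed on the subset of eligible patients who received at least 1 dose of study drug".

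Appendix C section 3.9 says that every participant given study treatment is evaluated for safety, which agrees with 13.6.1. Section 1.3 makes safety a secondary objective across all enrolled disease groups: "To examine the safety and toxicity of pembrolizumab in patients with biologically selected subsets of R/R lymphoma and histiocyte/dendritic cell neoplasms". Section 13.1 words the scope more narrowly: "We will also describe the safety and toxicity of pembrolizumab in patients with biologically selected subsets of relapsed and refractory diffuse large B-cell lymphoma".

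On discontinuation, 13.6.1 ends its list of separately reported items with: "other safety-related events resulting in discontinuation from study will be reported separately". Section 5.5 lists an unacceptable adverse event as a reason to stop protocol therapy. Section 5.6 keeps such patients in follow-up until the event resolves or stabilises. Section 5.7 gives the reasons for leaving the study as completion, loss to follow-up, withdrawal of consent and death.

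**The concern.** Whether a patient met the entry criteria has no bearing on whether the drug harmed them, so a safety denominator normally includes everyone exposed. The word *eligible* in 13.7 removes exposed patients, and it stands in the section on exclusions, where an analyst would look for the rule. Section 13.7 does not say who rules on eligibility or when, so the choice between the two populations could be made after the events are known. With roughly 30 patients, one or two exclusions move a rate by a visible amount.

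The discontinuation wording raises a different problem. The share of patients who stop treatment for toxicity is a basic tolerability result. The sentence in 13.6.1 names a different event, departure from the study, which the protocol records separately.

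**Working it through.** **1. The plan's own figure.** The only numerical statement on toxicity is in 13.2.2: a maximal 90% interval of about ±20 points. The exact (Clopper-Pearson) 90% interval for 10 of 20 has lower limit Beta(0.05; 10, 11) = 30.2% and upper limit Beta(0.95; 11, 10) = 69.8%. The half-width is (69.8 − 30.2)/2 = 19.8 points, so the figure reproduces. The response rule in the same paragraph (at least 6 of 20; 15% against 40%) gives a one-sided alpha of 0.0673 and power of 0.8744, in line with the stated 0.07 and 87%. Neither depends on the safety population.

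**2. The two populations side by side.**

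| Section | Dosing condition | Eligibility condition |
|---|---|---|
| 13.6.1 | at least one dose | none |
| Appendix C 3.9 | received study treatment | none |
| 13.7 (toxicity) | at least one dose | must be eligible |

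The sets differ exactly by the patients who were treated but are not eligible.

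**3. Can such patients exist?** Yes. Appendix C section 3.8.2 defines a protocol exception, giving as its example "enrollment of a participant who does not meet all inclusion/exclusion criteria", and section 3.7.3 of that appendix permits exceptions with approval of the lead IRB. Ineligibility may also surface after dosing. Section 4.3 expects outside sites to start therapy within 5 days of registration, while Appendix C section 5.1 allows 30 days from enrolment to forward eligibility packets for source verification. Eligibility is also checked before registration, so the number may be small or zero.

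**4. Size.** Let N be the number treated, x the number with a given event, and k the number treated but ruled ineligible. All treated: x/N. Under 13.7 the result lies between (x − k)/(N − k), if all dropped patients had the event, and x/(N − k), if none did. Section 13.2.1 expects 24 to 30 patients, with six histiocytic/dendritic patients besides, so N of 24 to 36 covers the range. The values x = 6 and k = 1 to 3 are assumptions.

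| N | k | All treated | All dropped had the event | None did |
|---|---|---|---|---|
| 30 | 1 | 6/30 = 20.0% | 5/29 = 17.2% | 6/29 = 20.7% |
| 30 | 2 | 6/30 = 20.0% | 4/28 = 14.3% | 6/28 = 21.4% |
| 30 | 3 | 6/30 = 20.0% | 3/27 = 11.1% | 6/27 = 22.2% |
| 24 | 2 | 6/24 = 25.0% | 4/22 = 18.2% | 6/22 = 27.3% |
| 36 | 2 | 6/36 = 16.7% | 4/34 = 11.8% | 6/34 = 17.6% |

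**5. Discontinuation.** A patient whose therapy ends for an unacceptable adverse event is off therapy under 5.5 and still followed under 5.6. Nothing in 5.7 takes that patient off study on account of the event. The patient therefore does not meet the literal description in 13.6.1 unless they also leave the study for another reason. The right data are already collected: 5.5 requires the reason for and date of stopping therapy on the case report form, and Table 4 in 7.3.4.4 asks, for each adverse event, whether it caused the product to be discontinued.

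**The case against.** The strongest reply is that the dedicated safety section already states the all-treated rule and Appendix C supports it, so a sensible analyst would follow those two statements over one general sentence in 13.7. The number of treated but ineligible patients may be zero, and a shift of about 6 points is well inside the stated ±20. This limits the importance but does not remove the contradiction. The ±20 describes sampling error, and it gives no reason to leave the denominator open.

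Several stronger readings are tempting, and the documents do not support them.

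- *A third safety population.* A reader might take 13.1 as a DLBCL-only analysis set that excludes T-cell lymphoma and the histiocytic/dendritic patients. Section 13.1 is an endpoint summary. It sets no dosing condition and no exclusion, and it reads as wording left from a narrower scope. It should be aligned with 1.3, but no share of patients can be counted as excluded by it. Nor is 13.5 a safety set: its rule begins "Primary and secondary analyses will be performed on all patients who had measurable disease present at baseline" and concerns response-evaluable patients, without mentioning safety.
- *Patients treated before registration.* Section 4.1 says: "Any participant not registered to the protocol before protocol therapy begins will be considered ineligible and registration will be denied". Such a person never enters the study, so the exclusion does not come from 13.7.
- *Downward bias.* A reader might infer that patients enrolled by exception are frailer, so that toxicity is understated. No passage says so, and the calculation runs both ways.
- *An empty discontinuation table.* Section 5.7 does not list adverse events, but it forbids nothing. Withdrawal of consent may follow toxicity, and 5.4.1 and 5.4.4 remove patients from the trial or study for further reasons. SAEs and deaths read as separate items, reported whether or not anyone discontinues. The category is incomplete, not empty, and nothing directs that a rate near zero be reported.

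**Conclusion.** Sections 13.6.1 and 13.7 contradict each other on who counts for toxicity, and 13.7 is the outlier. Following it would drop exposed patients. In the illustration, 20.0% becomes 14.3% or 21.4% with 30 treated, 6 events and 2 dropped; these counts are assumed, because the documents give none, and the direction is not determined. The discontinuation sentence is a separate mismatch with 5.5, 5.6 and 5.7. Read literally, it would miss most treatment stops for toxicity, on the understanding that patients who stop for an adverse event usually stay in follow-up as 5.6 provides. The primary endpoint and its operating characteristics are untouched. Both points should be corrected before safety data are analysed, since they affect a stated secondary objective.

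**What to change.** 1. In 13.7, delete *eligible* for toxicity analyses, so that one safety set applies throughout: all enrolled patients who received at least one dose, regardless of eligibility or histology.
2. In 13.6.1, report events leading to discontinuation of protocol therapy, using the reason and date required by 5.5 and the action-taken item in Table 4. Departures from the study can be listed separately under the 5.7 reasons.
3. In 13.1, widen the safety sentence to the scope of objective 1.3.

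The cost is three wording changes, with no new data and no change to design or treatment. Reported toxicity may be slightly less favourable.
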